## 1.0 INTRODUCTION

### 1.1. Background and Significance

Atrial fibrillation (AF) is the most common, sustained heart rhythm disorder experienced by humans. It is anticipated that more than 10 million individuals in the United States will have AF by 2050.[1] This is concerning as AF is associated not only with complications including heart failure, stroke, and premature death, but also troubling symptoms such as palpitations, dyspnea, and fatigue.[2] As a result, the burden of AF-related symptoms and complications on affected individuals and society is growing, as represented by increasing hospitalizations and healthcare costs.[3] There is thus a pressing need to characterize modifiable factors that may reduce the incidence, prevalence, and overall impact of AF.

Coffee is one of the most ubiquitously consumed substances worldwide. In addition to caffeine, coffee contains a variety of other biologically active compounds.[4] Correspondingly, whether any effect of coffee on health outcomes exists is of considerable interest to physicians, scientists, and individual consumers. While significant data exist on the potential impact of coffee on many cardiometabolic parameters, [4] there is conflicting data on any role of coffee on AF.[5] Given both the increasing population impact of AF and the widespread use of coffee in society, determining even a modest associated benefit or risk would be of great clinical relevance.

### 1.2. Possible Mechanisms of Coffee and its Constituents

Amongst the constituent compounds in coffee, the majority of prior research has focused on caffeine. While the caffeine content of coffee varies significantly, an average cup is estimated to contain between 95 and 200mg of caffeine.[6] Caffeine is a methylxanthine alkaloid and a potent central nervous system stimulant. It also exerts a range of cardiovascular effects that may facilitate atrial arrhythmogenesis. This includes sympathetic stimulation, enhanced automaticity, and increased after depolarization-induced triggered activity.[5] Conversely, caffeine also has mechanisms that might reduce AF; for example, caffeine inhibits adenosine which can trigger AF, and it additionally has some antioxidant activity. Finally, it has been estimated that coffee contains over 1,000 compounds, including some with described biological effects such as diterpene alcohols and chlorogenic acid.[4] As a result, there are plausible mechanisms for coffee and its constituents to have both beneficial and harmful cardiovascular and arrhythmic effects.

### 1.3. Prior Observational Studies on Coffee, Caffeine, and AF

A number of prior observational studies have evaluated the role of chronic coffee consumption and incident AF with varied results. In the Multifactor Primary Prevention Study, moderate coffee consumption of 1-4 cups per day was associated with increased risk.[7] Similarly, intermittent coffee consumption of less than 0.5 cups/day appeared to be associated with greater AF risk in the Multi-Ethnic Study of Atherosclerosis.[8] In contrast, several reports have found no clear relationship between coffee or caffeine intake and incident AF. These include reports from the Danish Diet, Cancer, and Health Study,[9] the Framingham heart Study,[10] two Cohort of Swedish Men,[11] and the Swedish Mammography Cohort.[11] Conversely, other studies have described results potentially consistent with a linear benefit of increasing coffee consumption. These include reductions of risk in hospitalized Kaiser Permanente patients,[12] an updated analysis from the Danish Diet, Cancer, and Health Study,[13] an Italian cohort,[14] and the UK Biobank.[15] Finally, a few investigators have demonstrated J- or U-shaped associations with benefit at modest intakes no effect or harm at higher levels, such as that seen in the Women's Health Study,[16] Physicians' Health Study,[17] the Seguimiento Universidad de Navarra (SUN) cohort,[18] and the Prevencion con Dieta Mediterranea (PREDIMED) cohort.[18] Meta-analyses including the aforementioned studies have concluded either no effect or a reduced AF risk with coffee consumption.[11, 19, 20] Furthermore, Mendelian randomization techniques using alleles associated with caffeine metabolism and hence coffee consumption have also not provided supportive evidence for any significant effect on AF.[15, 21]

Comparatively fewer studies exist on the role of acute coffee or caffeine ingestion, or on AF and related outcomes in other settings. One study found that acute intravenous administration of caffeine did not alter invasive measures of cardiac conduction or refractoriness.[22] Two reports suggest that modest coffee consumption may

be associated with a greater likelihood for spontaneous cardioversion compared to higher consumption.[23, 24] Furthermore, no association between caffeine intake and atrial ectopy was found in another analysis from the Cardiovascular Health Study.[25]

#### **1.4. Current Consumer and Physician Beliefs**

Despite the varied evidence described above, established notions exist that coffee and caffeine contribute to AF and/or trigger AF episodes. In a large study of symptomatic patients with paroxysmal AF, caffeine was reported as the second most common triggering factor in almost one-third of individuals.[26] Prior surveys of physicians have also suggested reductions in caffeine to assist with arrhythmias.[27] Conversely, professional society guidelines either do not discuss coffee or caffeine [28] or suggest they are unlikely to contribute based on recent studies.[29]

#### **1.4. Rationale for Current Study**

A key limitation of existing data on the effects of coffee and caffeine on AF has been their observational nature. Even with careful study design methodology, including prospective data collection, comprehensive characterization of participants, and appropriate analytical techniques, it is challenging if at all feasible to eliminate the possibility of biases in observational studies such as residual confounding and reverse causality.[30] Instead, appropriate randomization of subjects to an exposure of interest is more likely to produce reliable, unbiased results where observational evidence is conflicting or requires confirmation.[31] To the best of our knowledge, no such assessment on the effect of coffee on AF outcomes has been undertaken to date.

While the general effect of coffee or caffeine on incident AF would be of significant interest, undertaking a randomized trial in this setting would be challenging and likely to require an extremely large number of otherwise healthy individuals to agree to consume or abstain. Many individuals may find this objectionable given the widely consumed nature of coffee and caffeine-containing substances.

An alternative and potentially more practical setting would be in patients with existing AF who are not only at higher risk for (recurrent) AF episodes but may be more likely to be interested in such a randomized evaluation given their personal situation.

Thus, this study proposes to evaluate the effect of random allocation to coffee abstinence compared to continued caffeinated coffee consumption in patients undergoing cardioversion for AF, with patients being followed up for recurrent episodes of AF.

This study will provide the first, randomized evaluation of coffee on AF outcomes. Given the conflicting evidence to date and widespread consumption of coffee, this study will be of significant interest to consumers and physicians alike.

## 2.0 INVESTIGATIONAL PLAN

### 2.1 Study Design

This study is an investigator-initiated, prospective, open-label, randomized (1:1) clinical trial of coffee abstinence compared to coffee continuation on recurrent AF in patients undergoing cardioversion.

This study will be conducted at the coordinating center in the United States (the University of California, San Francisco), in Australia (University of Adelaide), and in Canada (Sunnybrook Health Sciences Centre). Two-hundred (200) participants total will be enrolled and randomized.

#### 2.1.1 Study Visits and Windows

After screening and eligibility has been determined, participants will be enrolled and randomized at the baseline visit (date of cardioversion).

No in-person follow-up visits will be required. Phone call follow-ups will be conducted at week 1, month 1, month 3, and month 6 until first recurrence of AF or study completion (whichever comes first). This will be supplemented with chart review, including scanned medical records if the patient does not return for medical care, and analyses of ECG strips obtained from AliveCor (San Francisco, CA) KardiaMobile devices and Apple Watch (Cupertino, CA) devices already owned and in use by patients.

Table 1 outlines the window for each of the study visits. Clinical sites should make every possible effort to ensure that each study visit is conducted within the specified window.

[figure not shown]
**Table 1. Visit Windows**

Study Visit	Scheduled Timepoint	Visit Window
V1a-V1b (Screening)		
V1c (Baseline)	Enrollment/Cardioversion	
V2	Month 1*	+/- 7 days
V3	Month 3*	+/- 7 days
V4	Month 6*	+/- 14 days

*\*Follow-up visits will be calculated from the date of cardioversion (i.e., baseline).*

In the occasional event that routine clinical pre-operative care does not allow adequate time for study coordinators to approach potentially eligible patients for the baseline visit prior to their cardioversion procedure, study coordinators may call patients who were successfully cardioverted to normal sinus rhythm within a week after their cardioversion procedure to see if they are interested in participating. Visits V1a-V1c will be carried out remotely in this case. In this occasional remote situation, if a patient chooses to take part in the study, informed consent will be obtained through Docusign and they will be randomized to either continue or abstain from coffee. Phone call follow-ups Visits V2-V4 will accordingly be conducted at month 1, month 3, and month 6 until first recurrence of AF or study completion (whichever comes first).

**Figure 1. Study Flow Diagram**

## 2.2 Study Objectives

The objectives of this clinical trial are to assess the effect of abstaining from coffee compared to continuation of coffee on the first recurrence of AF following cardioversion.

### Primary objectives:

- To assess the number of people with first confirmed clinical recurrence of AF or atrial flutter, or device-detected recurrence lasting longer than 30 seconds, following cardioversion in the coffee abstinence group compared to the continued caffeinated coffee consumption group analyzed as a time-to-event outcome

### Secondary exploratory objectives include assessment of the following:

- Adverse events before censorship, including myocardial infarction, stroke or transient ischaemic attack, heart failure exacerbation, syncope, emergency department visit, hospitalization, and death
- Atrial flutter and atrial fibrillation separately as incident outcomes

## 2.3 Inclusion/Exclusion Criteria

### 2.3.1 Inclusion Criteria

Patients must meet **all** of the following to be eligible:

1. Men or women ≥ 21 years of age
2. Sustained atrial fibrillation or atrial flutter (provided patient has history of atrial fibrillation)
3. Planned/scheduled direct current electrical cardioversion
4. Consumption greater than or equal to one cup of coffee per day sometime in the past 5 years
5. Willing and able to comply with coffee abstinence or continuation for at least 6 months
6. Life expectancy of at least 6 months
7. Willing and able to return and comply with scheduled phone follow up visits
8. Willing and able to provide written informed consent

### 2.3.2 Exclusion Criteria

Patients will be excluded if they meet **any** of the following:

1. Established allergy or adverse reaction to coffee
2. Stated inability to comply with coffee abstinence or continuation
3. Atrial fibrillation ablation in preceding 3 months or planned in next 3 months
4. Recent cardiothoracic surgery in preceding 3 months
5. Pregnancy or desire to get pregnant within next 6 months.
6. Current enrollment in an investigation or study of a cardiovascular device or investigational drug that would interfere with this study
7. Any other criteria, which would make the patient unsuitable to participate in this study as determined by the Principal Investigator (e.g., an uncontrolled drug and/or alcohol addiction)

## 3.0 STUDY TREATMENT

After eligibility for the study has been confirmed, participants will be randomized to abstinence from coffee or continued consumption of caffeinated coffee. Participants will undergo this intervention until the primary endpoint of AF recurrence, end of study (month 6), or study withdrawal, after which they will consume or abstain from coffee at their discretion.

### 3.1 Coffee Abstinence

If allocated to coffee abstinence, patients will be encouraged to completely abstain from coffee and other caffeine-containing products as much as feasibly possible. As some decaffeinated coffee can also contain caffeine, patients will be encouraged to abstain from decaffeinated coffee as well. Other non-coffee caffeine-containing products to

avoid will include, but not be limited to, tea, cola, energy drinks, chocolate, chewing gum, and chocolate- or coffee-flavored foods (e.g. ice cream).

### **3.2 Continued Coffee Consumption**

If allocated to continued coffee consumption, patients will be encouraged to drink at least one cup of caffeinated coffee (or one espresso shot) daily and other caffeine-containing products as per their usual lifestyle. It will be recommended that patients do not intentionally increase or decrease consumption of these products.

## **4.0 EARLY TERMINATION**

If a randomized participant terminates participation in the study early (i.e., prior to completion of all follow-up), the Principal Investigator will determine the primary reason for early termination and report this. Participants who early terminate from the study will not be replaced with newly enrolled participants.

### **4.1 Randomized Participants – with exclusion found on day of cardioversion**

A proportion of patients scheduled for electrical cardioversion do not convert to sinus rhythm, outlined in more detail below. Thus, randomization will be undertaken after successful cardioversion from AF to sinus rhythm in order to minimize exclusion of randomized patients for this reason.

In the event that another exclusion criterion is identified on the day of cardioversion after randomization has occurred, the participant may or may not continue to be treated as allocated as deemed appropriate by the Principal Investigator. All randomized patients will be included in the ITT analyses.

### **4.2 Unsuccessful cardioversion**

Patients will be interviewed and consented prior to cardioversion occurring. However, a small proportion of patients do not have successful cardioversion. As a result, randomization will occur after successful cardioversion from AF to sinus rhythm. Patients will be excluded in the event that cardioversion is unsuccessful.

### **4.3 Participant Withdrawals**

Each participant will be informed that participation in the study is voluntary and that he/she may withdraw from the study at any time without effect on subsequent medical treatment or relationship with the treating physician. Participants who discontinue follow-up at any time after randomization will be included in the ITT analyses.

### **4.4 Other Early Terminations**

Participants who discontinue follow-up at any time after randomization will be included in the ITT analyses.

**Lost to Follow-Up:** If a participant is unable to be contacted via phone for follow-up (i.e. participants who become lost to follow up and whose status is unclear because they fail to appear for study visits without stating an intention to withdraw) for any other reason and the study team is unable to confirm the status of their atrial fibrillation post-cardioversion upon review of their medical record at study follow up visits, the participant will be designated an early termination. The clinical site Principal Investigator should show "due diligence" by documenting in the source documents, all steps taken to contact the participant, e.g., dates of telephone calls, registered letters, etc.

In the absence of a stated intention to withdraw, the physician or other healthcare professional of participants may be contacted in an attempt to ascertain the presence or absence of AF recurrence.

**Principal Investigator Determination:** Participants should also be early terminated at any time if the Principal Investigator concludes that it would be in the participant's best interest for any reason. Protocol deviations should not lead to early termination unless they indicate a significant risk to the participant's safety.

**Early Study Closure:** The study may be terminated due to safety concerns. Should this be necessary, participants currently in follow-up will be early terminated and scheduled for a Close-Out Visit, as soon as possible. The Principal Investigator will be responsible for informing the appropriate local Institutional Review Board of the early study termination.

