### 10.2 Intention-to-Treat (ITT)

The main intention-to-treat (ITT) analysis set will include all randomized participants, whether or not they are compliant with the treatment allocation for this trial. Every attempt will be made to collect data until the end of the follow-up period for all randomized participants and these data will be included as part of the main ITT analysis. The analyses for the primary objective will be performed using the ITT dataset.

Although substantial crossover is not anticipated, as treated and per protocol analyses will also be conducted if failure to comply with allocated treatment assignments occurs in more than 10% of cases or if there is a significantly different proportion of assignment adherence in one group compared to the other.

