### **6.0 STATISTICAL METHODS**

All analyses will be conducted upon completion of data collection and database lock. No interim analyses are planned.

The primary analysis will be by intention-to-treat (ITT), according to randomized allocation, without regard to participant compliance with this randomized allocation. Every attempt will be made to collect data for both primary and secondary endpoints until the end of the six month follow-up period for all randomized participants, and all data will be included as part of the primary ITT analysis.

Although substantial crossover is not anticipated, as treated and per protocol analyses will be conducted if failure to comply with the randomized allocation occurs in more than 10% of all participants or if there is a significantly different proportion of assignment adherence in one group compared to the other. The per protocol analyses will be restricted to a sub-sample excluding all the protocol violators, and adjust for any baseline factors that are imbalanced ( $P<0.1$ ) in the per-protocol sub-sample.

Patient baseline characteristics will be summarized overall and by randomization assignment. Continuous variables will be summarized using means and standard deviations (SD) for normally

distributed measures or medians and quartiles for non-normally distributed measures. Categorical variables will be summarized using contingency tables that display counts and percentages.

All tests will be two-sided with a 0.05-level of significance. Adjustment for multiple comparisons will not be used.

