## **6.1 PRIMARY ENDPOINT ANALYSIS**

The primary endpoint, defined as the clinical recurrence of AF or device-detected AF lasting longer than 30 seconds, will be analyzed as a time-to-event outcome. Follow-up time for participants who do not experience the primary endpoint will be censored at the time of study withdrawal or end of study (month 6). Kaplan-Meier plots will be used descriptively to compare the survival distributions of the primary endpoint by randomization arm. Cox proportional hazards regression models including the randomization assignment will be used to formally analyze the primary endpoint (AF recurrence). These models will also include study site, used in the randomization procedure as a stratification factor, and additionally baseline patient characteristics in sensitivity analyses. Point estimates and Wald-based 95% confidence intervals and p-values will be reported. The primary ITT analysis will include all participants regardless of compliance with randomized allocation.

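### Protocol 4.4 ends participation for investigator-determined terminations, while Protocol 10.2 and SAP 6.0 promise six-month data on everyone randomized; the two must be reconciled and the censoring rule stated

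*Combined protocol and SAP*

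**What the plan says.** Under Principal Investigator Determination, Protocol 4.4 says "Participants should also be early terminated at any time if the Principal Investigator concludes that it would be in the participant's best interest"; no specific ground is required. The next sentence narrows this: "Protocol deviations should not lead to early termination unless they indicate a significant risk to the participant's safety".

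Protocol 4.0 describes the participant concerned as one who "terminates participation in the study early (i.e., prior to completion of all follow-up"), and asks the investigator to report the main reason. Section 4.4 uses the term in the same sense for people lost to follow-up and for early closure of the study.

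Other sections point the other way. Protocol 10.2: "Every attempt will be made to collect data until the end of the follow-up period for all randomized participants". SAP 6.0 makes the same commitment for primary and secondary endpoints, "until the end of the six month follow-up period for all randomized participants, and all data will be included". Protocol 4.4 also says "Participants who discontinue follow-up at any time after randomization will be included in the ITT analyses".

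On censoring, SAP 6.1 has follow-up without a primary event "censored at the time of study withdrawal or end of study (month 6"). It does not mention investigator-determined termination. The adverse event endpoint (Protocol 2.2, SAP 2.0 and 6.2) counts only events that occur before censoring.

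The trial is open-label (Protocol 2.1). SAP 4.2 discusses blinding of participants only, and neither document describes blinding of the investigator.

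**The concern.** For a participant whom the investigator terminates for best-interest or safety reasons, a site reading 4.0 and 4.4 would end participation, and a site reading 10.2 would carry on collecting data. The plan does not say which governs.

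If follow-up ends, recurrences, hospitalizations and deaths after that date are not sought. Keeping the person in the intention-to-treat set does not supply outcomes that nobody observed. The Cox model in SAP 6.1 would treat the missing time as uninformative, and the SAP plans no sensitivity analysis for informative censoring.

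That assumption is weak here. The decision is discretionary, the investigator is not described as blinded, and the reason for it is the participant's welfare. Terminations could therefore be more frequent in one arm and concentrated in people with a different recurrence risk. With both conditions, the estimate is no longer the intention-to-treat effect that 10.2 describes.

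**Working it through.** **1. The passages side by side.**

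| Question | Protocol 4.0 and 4.4 | Protocol 10.2, SAP 6.0 |
|---|---|---|
| Who is covered | Best-interest or safety terminations by the investigator | All randomized participants |
| What happens to follow-up | Participation ends before follow-up is complete | Every effort to collect data to the end of follow-up (six months in the SAP) |
| Primary analysis | Kept in the ITT set | Kept in the ITT set |
| Censoring date (SAP 6.1) | Not stated | Month 6 if event-free |

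SAP 6.1 offers two censoring points. Someone whose observation stopped at month 1 is either treated as a study withdrawal and censored then, or carried event-free and unobserved to month 6. The first is the more likely reading. It is an inference, not a stated rule.

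**2. The plan's power figure.** Protocol 10.1 and SAP 5.0 give about 80% power for a hazard ratio of 1.63 with 100 per arm, 50% recurrence and 10% loss. The table in Protocol 10.1 is reproduced by taking the recurrence rate in the lower-risk arm, applying the hazard ratio to the other arm, and counting losses as half:

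- Events D = 100 × 0.95 × (0.5 + 1 − 0.5^1.63) = 95 × 1.177 = 111.8.
- Power = Φ(√111.8 / 2 × ln 1.63 − 1.96) = Φ(0.62) = 0.733.

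The stated 80% is therefore not reproduced at 50% recurrence; 1.63 is the table's 60% entry at 10% loss. That is a separate matter. I use 0.733 only as a baseline.

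**3. Power cost.** Assume exponential recurrence with 50% at six months, a hazard of ln 2 / 6 = 0.1155 per month. A participant terminated at month 1 loses exp(−0.1155) − 0.5 = 0.391 expected events.

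| Participants terminated | Events lost | Power for 1.63 |
|---|---|---|
| 0 | 0 | 0.733 |
| 5 | 2.0 | 0.726 |
| 10 | 3.9 | 0.718 |
| 20 | 7.8 | 0.702 |

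**4. Bias.** The documents give no number, timing, arm or prognosis for these terminations, so the following are assumptions:

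- no true effect;
- 50% six-month recurrence in ordinary participants;
- a fraction p of each arm with r times their hazard λ;
- in the abstinence arm only, that fraction is censored at 0.08 of follow-up (0.08 × 6 = 0.48 months, about two weeks).

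After that time the abstinence arm has hazard λ. With t measured in units of six months and λ = ln 2, the coffee arm has

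λ × [(1−p)e^(−λt) + p r e^(−rλt)] / [(1−p)e^(−λt) + p e^(−rλt)].

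For p = 0.10 and r = 3:

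- At t = 0.08 the multiplier is (0.851 + 0.254) / (0.851 + 0.085) = 1.18, so the hazard ratio is 1 / 1.18 = 0.85.
- At t = 1 it is (0.450 + 0.0375) / (0.450 + 0.0125) = 1.054, so the hazard ratio is 0.95.
- Before 0.08 it is 1.00.

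Solving the large-sample Cox score equation over the whole period gives:

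| Share of one arm terminated | r = 1 | r = 1.5 | r = 2 | r = 3 |
|---|---|---|---|---|
| 5% | 1.00 | 0.98 | 0.97 | 0.95 |
| 10% | 1.00 | 0.96 | 0.94 | 0.91 |

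Holding overall recurrence at 50% instead leaves the range at 0.98 to 0.91. A second scenario, with termination at month 1 and an 80% six-month risk in those terminated (relative hazard −ln 0.2 / ln 2 = 2.3), gives null rate ratios of 0.985, 0.967 and 0.938 for 2%, 5% and 10%. If the terminations fall in the coffee arm, the direction reverses.

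**5. Scale.** With about 100 events, the standard error of the log hazard ratio is about 2 / √100 = 0.20. The shifts are ln 0.98 = −0.020 and ln 0.91 = −0.094, or 0.1 to 0.5 standard errors.

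**The case against.** The strongest reply is that 4.4 is narrower than it looks. Its next sentence keeps participants who merely deviate in the study, so someone allocated to abstinence who resumes coffee is by default followed and analysed as randomized. That stands. A reader might infer that stopping the allocation and stopping observation are always the same act; the documents do not support this, and the conflict is confined to best-interest or safety terminations.

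Other tempting readings also fail:

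- Protocol 4.1, where "the participant may or may not continue to be treated as allocated as deemed appropriate by the Principal Investigator", does not contradict 4.4. It concerns an exclusion criterion found on the day of cardioversion. It does show that the protocol can accommodate someone off allocation who stays in the analysis.
- Nothing makes a myocardial infarction or heart failure event a trigger for termination. Section 5.8 lists these as events to record.
- Caffeine withdrawal is not the only risk named. Section 6.2 also raises possibly greater recurrence with abstinence.

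It can further be said that a best-effort commitment coexists with rare terminations, and that outcomes also come from chart review and device recordings (2.1.1). This is fair, but 4.4 does not say that these sources stay in use after an investigator's termination. It does provide for record review and contact with the treating professional when a participant is lost, and 9.2 seeks vital status even after authorization is revoked. Investigator-terminated participants have no such provision.

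Finally, the bias scenario needs 5 to 10 people out of 100, all in one arm, with raised risk. The documents give no basis for expecting that many, so the figures are illustrative only.

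**Conclusion.** The conflict is real and limited. For investigator-determined terminations, Protocol 4.0 and 4.4 end participation, while Protocol 10.2 and SAP 6.0 require continued data collection. SAP 6.1 does not say how such participants are censored.

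A reader might infer that the plan mandates the loss of follow-up and the censoring. It does not: the first is one of two conflicting instructions, and the second is the likeliest reading of a silent rule.

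Bias requires both an imbalance between arms and a different recurrence risk in those terminated. Under the assumed 5-10% of one arm at about two weeks and 1.5-3 times the hazard, the null hazard ratio moves to about 0.98-0.91. With average risk it stays at 1.00. Power falls by at most about three percentage points with 20 terminations. The effect on the adverse event comparison cannot be sized from the documents. The shift is modest against sampling error, but it is systematic, could favour either arm, and is cheap to prevent.

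**What to change.** Reconcile Protocol 4.4 with Protocol 10.2 and SAP 6.0. State that an investigator's decision to stop the allocation does not end observation. The month 1, 3 and 6 calls (to first recurrence or month 6, as for everyone), record review and adverse event collection continue unless the participant withdraws consent or cannot be traced.

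In SAP 6.1, define study withdrawal for censoring as withdrawn consent or loss to follow-up, and report investigator terminations by arm, timing and reason. Reasons are already to be recorded under 4.0. If data collection is complete, the SAP can still define the handling of these participants and report them before database lock.

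Whether and when to stop the allocation remains the investigator's decision; nothing here changes it. The cost is wording in both documents, one CRF field and a few extra phone calls, with no in-person visits.
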